#### 6.11.3. Additional Analyses of the Primary Outcome

The primary MMRM analysis model will be repeated using the PP and Completer populations as a sensitivity analysis. If the conclusion differs from that of all randomized patients, the data and analyses will be further investigated.

A secondary analysis model will be an ANCOVA for HbA1c change from baseline to the study primary endpoint, using the model with strata (country, type of basal insulin, use of metformin at study entry) and treatment as fixed effects and baseline as a covariate. Missing endpoints will be imputed using the LOCF approach using postbaseline data only.

#### 6.11.4. Sensitivity Analyses for Missing Data

There is no sensitivity analyses for missing data.

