The definitions of baseline and postbaseline for the efficacy and safety analyses depend on which analysis period is being used. The following analysis periods will be used:

- Lead-in Period Visits 2-8
- 26-Week Treatment Period from randomization to Week 26 prior to discontinuation of IP
- 26-Week Treatment Period and Safety Follow-Up Visit from randomization to Visit 801 (including all data regardless of IP use)

The data on IP is defined based on the following rules:

- for data only measured at an office visit
  - MMTT postbaseline data will be considered as data on IP if the MMTT performance date is on or prior to the last IP dose date
  - Other postbaseline data (for example, vital signs, laboratory tests, and questionnaires) will be considered as data on IP if the measurement date is on or prior to the cutoff date defined as 14 days after the last IP dose date
- for data collected as running records with an exact date stamp such as adverse events (AEs) and diary entries where the dates of the measures were not tied with the date of an office visit, postbaseline data with dates ≤ (last study drug dose date +1) will be considered as data on IP.

Table 6.2 describes the rules for determining the patient population, baseline and postbaseline observations for the different analysis periods.

For continuous measures, summary statistics will include sample size, mean, SD, median, minimum, and maximum for both the actual and the change from baseline measurements. Least-squares (LS) means and standard errors derived from the analysis models will also be displayed. Treatment comparisons will be displayed showing the treatment difference LS means and the 95% CIs for the treatment differences, along with the p-values for the treatment comparisons.

For categorical measures, summary statistics will include sample size, frequency, and percentages. Fisher's exact test will be used for treatment comparisons.

For laboratory values, Systeme International (SI) units will be presented. Therefore, both % and mmol/mol will be presented for HbA1c and mmol/L will be presented for glucose measurements.

All baseline measures will be analyzed using an analysis of variance (ANOVA) model that has treatment as the model terms.

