# Table 6.2.Baseline and Postbaseline Definitions and Patient Population by
Study Period and Type of Analysis

Study Period/Analysis	Patient Population	Baseline Observations	Postbaseline Observations
Lead-In Period			

TEAEs	All Enrolled Patients	Prior to first dose of open-label insulin lispro (or Visit 2 date if the dose date is missing)	The entire lead-in period after first dose of open-label insulin lispro and prior to the first dose of IP (or Visit 8 date if the dose date is missing)
Basal, prandial, and total insulin doses, and prandial/total insulin dose ratio	All Randomized Patients	Visit 2	Visits 3–8 prior to initiation of IP
Weight MMRM and ANCOVA	All Randomized Patients	Last of Visits 1-2	Visits 3–8 AND Last of Visits 3-8
26-Week Treatment P	Period (including Safety	Follow-Up Visit wher	e applicable)
HbA1c MMRM and ANCOVA	All Randomized Patients with a baseline and at least 1 postbaseline observation while on IP	Last of Visits 7-8	Visits 11, 13, 15, and 18 prior to discontinuation of IP AND Last of Visits 9-18 prior to discontinuation of IP

Study	Patient Population	Baseline	Postbaseline Observations
Period/Analysis		Observations	
HbA1c categorical analyses longitudinal logistic regression and LOCF logistic regression	All Randomized Patients with a baseline and at least 1 postbaseline observation while on IP	Last of Visits 7-8	Visits 11, 13, 15, and 18 prior to discontinuation of IP AND Last of Visits 9-18 prior to discontinuation of IP
1-hr and 2-hr PPG and other MMTT variables	All Randomized Patients with a postbaseline observation while on IP	Visit 8 prior to initiation of IP	Visit 18 prior to discontinuation of IP
10-point SMBG, basal, prandial, and total insulin doses, prandial/total insulin dose ratio	All Randomized Patients with a baseline and at least one postbaseline observation	Visit 8 prior to initiation of IP	Visits 15, and 18 prior to discontinuation of IP AND Last of Visits 9 to 18 prior to discontinuation of IP
1,5-AG	All Randomized Patients with a baseline and at least 1 postbaseline observation	Visit 8 prior to initiation of IP	Visits 11, 15, and 18 prior to discontinuation of IP AND Last of Visits 9-18 prior to discontinuation of IP
Health outcomes: ITSQ, EQ-5D-5L, EQ-VAS, WPAI-GH	All Randomized Patients with a baseline and a postbaseline observation	Last of Visits 1-8	Last of Visits 9-18 prior to discontinuation of IP

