Safety Laboratory Tests (chemistry, hematology, lipids) – continuous analysis	All Patients in the Safety Population with a baseline and a postbaseline observation	Last of Visits 1-8	Visit 18 (planned) AND Last of Visits 9-18 (planned including early discontinuation visits), regardless of IP use
Safety Laboratory Tests (chemistry, hematology, lipids) – categorical analysis	All Patients in the Safety Population with a normal baseline (with respect to the direction being analyzed) and a postbaseline observation	Visits 1 -8 (including unplanned tests)	Visits 9-18 (including unplanned tests), regardless of IP use

Study	Patient Population	Baseline Observations	Postbaseline Observations
Period/Analysis			
TEAEs	All patients in the Safety Population	Prior to first dose of randomized IP (or Visit 8 date if missing) and after the first dose of open-label insulin lispro (or Visit 2 date if missing)	From first dose of randomized IP to last dose of randomized IP AND From first dose of randomized IP to Visit 801
Hypoglycemia events	All patients in the Safety Population	All Visits 2-8	All Visits 9-18 prior to discontinuation of IP
Weight and vital signs	All Patients in the Safety Population with a baseline and a postbaseline observation	Last of Visits 2-8	Visits 9-18 prior to discontinuation of IP AND Visits 9-801 regardless of IP use
Anti-insulin lispro antibody	Safety Population	Visit 2	Visits 3-801 regardless of IP use

Baseline and Postbaseline Definitions and Patient Po	pulation by Study	v Period and Type of Analysis
Buschne und i ostbuschne Demittons und i utent i	pullution by Stud	j i ci ioù una i jpe oi i inaijsis

Abbreviations: 1,5-AG = 1,5-Anhydroglucitol; ANCOVA = analysis of covariance; EQ-5D-5L = European Quality

of Life- 5 Dimensions 5 Level; EQ-VAS = EuroQol visual analogue scale; HbA1c = hemoglobin A1c; IP = investigational product; ITSQ = Insulin Treatment Satisfaction Questionnaire; ITT = intention-to-treat; LOCF = last-observation-carried forward; MMTT = mixed meal tolerance test; MMRM = mixed-effect model repeated measures; SMBG = self-monitored blood glucose; TEAE = treatment-emergent adverse event; WPAI-GH = Work Productivity and Activity Impairment General Health.

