#### 6.3. Handling of Dropouts or Missing Data

The analyses for the primary and multiplicity adjusted objectives will be performed on data collected prior to discontinuation of IP through Week 26.

Missing data will be addressed by using a mixed-effect model repeated measures (MMRM) analysis for continuous longitudinal variables. The MMRM model provides consistent estimator when data is missing at random. The model implicitly adjusts for missing data through a variance-covariance structure. An ANCOVA model will also be used to analyze continuous variables.

Unless otherwise stated, missing endpoints will be imputed using the last-observation-carried forward (LOCF) approach, using only postbaseline data, in the ANCOVA model.

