#### 6.11. Efficacy Analyses

#### 6.11.1. Primary Outcome and Methodology

The primary objective of this study (H1) is to test the hypothesis that LY900014 is noninferior to insulin lispro on glycemic control (NIM=0.4% for HbA1c) in patients with T1D, when administered as prandial insulin (0-2 minutes prior to the meal), in combination with basal insulin for 26 weeks.

The primary efficacy comparison will be based on the contrast between LY900014 and insulin lispro at Week 26 (Visit 18) from the MMRM analysis of change from baseline in HbA1c including data collected from all randomized patients prior to discontinuation of IP through Week 26. The model for the analysis of the primary efficacy endpoint of change from baseline in HbA1c will include the fixed class effects of treatment, strata (country, type of basal insulin, use of metformin at study entry), visit, and treatment-by-visit interaction, as well as the continuous, fixed covariates of baseline value. An unstructured covariance structure will be used to model the within-patient errors. Significance tests will be based on LS means and Type III tests. If this analysis fails to converge, the following covariance structures will be tested in order:

- Toeplitz with heterogeneity
- autoregressive with heterogeneity
- compound symmetry with heterogeneous variances
- Toeplitz
- autoregressive
- compound symmetry without heterogeneous variances

The first covariance structure that converges will be used. The Kenward-Roger approximation will be used to estimate denominator degrees of freedom.

LY900014 will be declared noninferior to insulin lispro if the upper limit of the 2-sided 95% CI for the LS mean difference in the change from baseline in HbA1c for LY900014 minus insulin lispro is below +0.4%.

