#### 7.6 Sensitivity Analysis for Efficacy

The impact of COVID-19 on the efficacy of IP on the patients may come from different aspects such as prolonged treatment interruptions due to COVID-19 illness or control measures, study or treatment discontinuations due to COVID-19 illness or control measures, death due to COVID-19 and the usage of protocol prohibited medications to treat COVID-19.

A sensentivity analysis will be conducted on the randomized patients without essential impact of COVID-19, i.e., the randomized patients who can't be classified into the above two groups. The MMRM and ANCOVA models as described in Section 6.11.1 and Section 6.11.3 respectively will be repeated as the models for the sensitivity analysis. If the conclusion differs from that of all randomized patients, the data and analysis will be further investigated.

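### Apart from LOCF and reruns that exclude patients, nothing planned tests graded departures from missing at random for H1 or shows where noninferiority would be lost

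*SAP*

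**What the plan says.** SAP 6.11.1 bases the H1 comparison on an MMRM "including data collected from all randomized patients prior to discontinuation of IP through Week 26". SAP 6.1 counts a laboratory value as on product if it is dated "on or prior to the cutoff date defined as 14 days after the last IP dose date". In SAP Table 6.2 the HbA1c analysis set is "All Randomized Patients with a baseline and at least 1 postbaseline observation while on IP", and the MMRM uses Visits 11, 13, 15 and 18 (Weeks 4, 8, 12 and 26).

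The justification is in SAP 6.3: "The MMRM model provides consistent estimator when data is missing at random". The whole of SAP 6.11.4 is: "There is no sensitivity analyses for missing data".

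Other analyses of the same endpoint are planned:

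- SAP 6.11.3 repeats the MMRM in the per-protocol and completer populations.
- SAP 6.11.3 also adds an ANCOVA in which "Missing endpoints will be imputed using the LOCF approach using postbaseline data only".
- SAP 7.6 adds a COVID-19 sensitivity analysis that "will be conducted on the randomized patients without essential impact of COVID-19".

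If the per-protocol, completer or COVID-19 rerun reaches a different conclusion, the SAP says only that the matter will be investigated further. The SAP reference list contains a paper on pattern-mixture models, but no method in the visible text uses it.

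**The concern.** SAP 6.11.2 places the full two-sided 0.05 on H1 and releases it to H2–H4 only once H1 is met. SAP 5.2 plans for 15% dropout, about 52 of 350 patients (0.15 × 350 = 52.5). HbA1c is not scheduled between Week 12 and Week 26. For a patient who stops product after Week 12 and before about Week 24, the model therefore predicts Week 26 from Week 12 or earlier. The observed data cannot confirm that prediction.

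If LY900014 patients who stop did worse than the model predicts, and lispro patients who stop did not, the MMRM would understate the difference in the direction that favours noninferiority. Reruns that drop patients cannot show this. LOCF puts one other fixed value in place of the missing one. A reader of the planned results would see a noninferiority conclusion without a planned statement of how strong a departure it survives.

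**Working it through.** **Inputs.** From SAP 5.2: margin 0.4, SD 1.1, no true difference, 149 completers per arm, stated power 87%, 15% dropout, 350 randomized. With 1:1 allocation this is 175 per arm. Actual missingness is not in the documents, so 15%, 10% and 5% are shown.

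**The plan's own figures.** SE = 1.1 × √(2/149) = 0.1274. With t(0.975, 296 df) = 1.968, the half-width is 0.251. Noncentral-t power at no difference is 87.9%, against the stated 87%. 298/0.85 = 350.6, against about 350. The sample size is not in error.

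**Tipping point.** Let D be the observed difference, p the fraction missing (equal in both arms), hw the half-width, and d_LY and d_Lis the amounts by which missing Week 26 values exceed the prediction under missing at random. The adjusted upper limit is D + p × (d_LY − d_Lis) + hw. It reaches 0.4 when d_LY = (0.4 − hw − D)/p + d_Lis. With n = 175 × (1 − p) per arm and d_Lis = 0:

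| p | SE | hw | D = 0 | D = +0.05 | D = +0.10 |
|---|---|---|---|---|---|
| 15% | 0.1275 | 0.2510 | 0.99 | 0.66 | 0.33 |
| 10% | 0.1240 | 0.2439 | 1.56 | 1.06 | 0.56 |
| 5% | 0.1206 | 0.2373 | 3.25 | 2.25 | 1.25 |

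Example: (0.4 − 0.2510 − 0.10)/0.15 = 0.33. If lispro discontinuers also depart by 0.2 or 0.4, that 0.33 becomes 0.53 or 0.73.

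**Error rate at the margin.** Assume d_LY = 0.4, d_Lis = 0 and a true difference, discontinuers included, of exactly 0.4. The value 0.4 for d_LY is chosen for illustration and appears nowhere in the plan. The MMRM then targets 0.4 − 0.4p, which is 0.34 at 15% missing. The chance of declaring noninferiority is P(T > t(0.975)), where T is noncentral t with noncentrality 0.4p/SE. This gives 6.8%, 5.1% and 3.6% at 15%, 10% and 5% missing, against a nominal 2.5%. With equal departures and equal dropout the shift is zero and the rate stays at 2.5%.

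**How often a +0.4 step in LY900014 only would change the reading**, with no true difference under missing at random. The chance that the upper limit is below 0.4 falls from 87.8% to 75.7% at 15% missing, from 89.6% to 82.5% at 10%, and from 91.1% to 88.1% at 5%. About 14%, 8% and 3% of noninferiority results would cross the margin (for example, (87.8 − 75.7)/87.8 = 13.8%).

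**Would the planned analyses reveal such a departure?** In 1,500 simulated trials (175 per arm, 15% missing, an assumed within-patient correlation of 0.7, on-product difference 0), LY900014 discontinuers were made 1.0 point worse after their last observed value. The true difference was 0.15. The likelihood estimate under missing at random, the completer estimate and the LOCF estimate were all about 0.00. This follows from the construction, since all three use only on-product data.

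**Check on the SE.** In 400 simulated trials with 50 imputations and a delta of 0.4 in LY900014, the mean shift was 0.0594 = (26/175) × 0.4. The mean multiple-imputation SE was 0.128, against 0.127 planned.

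**The case against.** A reader might infer that no planned analysis departs from missing at random. The documents do not support that: LOCF does not rest on the assumption, so one alternative is planned. It is fixed and ungraded, which is why the point is limited to graded departures and the tipping point.

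A reader might also infer that the MMRM is biased towards noninferiority. That is not supported either. The trial is double-blind, both arms use the same lispro concentration and titration targets, and Protocol 8.1 describes steps to limit missing data. Nothing suggests that discontinuers in one arm would do worse than predicted.

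Planned outputs do bear on dropout. SAP 6.6 compares discontinuation reasons by arm and time to discontinuation by log-rank test, and SAP 6.12.1 summarises days on study after stopping product. From these and the confidence interval a reader could approximate the tipping point with the formula above. That stands, but such summaries do not test the assumption, and a reader's approximation is not a prespecified analysis.

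Finally, the omission is disclosed and breaks no commitment, since Protocol 10.3.3.1.1 promises no missing-data stress test. That also stands. It makes this a robustness gap and not an inconsistency between the documents.

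**Conclusion.** The point holds as a gap in robustness assessment and should be fixed. The primary test, margin, alpha and sample size are not in question.

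Its size depends on missingness and on the observed difference. At 5% missing, or at an observed difference of 0 or below, only a large one-arm departure would matter: 0.99 points or more at an observed 0, even with 15% missing. At 15% missing and an observed +0.10, a departure of 0.33 is enough. The error-rate figures of 6.8%, 5.1% and 3.6% need both a true difference at the margin and an assumed one-arm departure of 0.4, so they are stress-test values and not expected rates. All figures assume the planned SD, equal missingness in the two arms and an SE unaffected by the shift.

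The off-product HbA1c collected under Protocol 8.1 does not carry this point. Using it would address a different treatment effect, could dilute the difference, and is not conservative for noninferiority.

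**What to change.** Before unblinding, replace SAP 6.11.4 with a delta-adjusted multiple-imputation tipping-point analysis of Week 26 HbA1c for H1:

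- **Analysis set.** Use the same patients as the primary MMRM (baseline and at least one on-product postbaseline value), so that the delta-0 cell is comparable with the primary result. State how randomized patients with no postbaseline value are handled.
- **Imputation.** Impute by arm under missing at random from baseline, strata and observed visits.
- **Grid.** Add delta to the imputed values in each arm separately, from 0 to at least +1.0 in steps of 0.2.
- **Reporting.** Combine by Rubin's rules and show where the upper 95% limit crosses +0.4%. State that the MMRM remains the primary decision.

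A minor clarification can go in at the same time. Table 6.2 names early-discontinuation visits in the safety-laboratory row ("Last of Visits 9-18 (planned including early discontinuation visits), regardless of IP use") but not in the HbA1c row. SAP 6.11.3 should say whether such an HbA1c, drawn within the 14-day window, enters LOCF.

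The cost is SAP text and modest programming, with no new data. The downside is that the robustness result may look less favourable than the primary result alone.

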#### 6.11.5. Other Secondary Efficacy Analyses

The longitudinal observations of actual and change from baseline in HbA1c up to Week 26 will be analyzed using the same MMRM model as for the analysis of the primary outcome. For the following secondary efficacy endpoints, an MMRM model similar to that for the primary outcome with an additional term of HbA1c stratum ( $\leq 8.5\%$ , >8.5\%) will be used:

- actual and change from baseline 1,5-AG values
- actual and change from baseline 10-point SMBG values (fasting, 1 hour post morning meal, 2 hours post morning meal, pre midday meal, 1 hour post midday meal, 2 hours post midday meal, pre evening meal, 1 hour post evening meal, 2 hours post evening meal, and bedtime)
- actual and change from baseline in total, basal, and prandial insulin doses and prandial/total insulin dose ratios

Three 10-point SMBG profiles are expected to be collected during the 2 weeks prior to specified visits. Valid SMBG profiles will be used for analysis, defined as having non-missing values at  $\geq 6$  time points among the 10 pre-specified time points and being collected 2 weeks prior to the given visit. For each time point, the average of the corresponding SMBG values from the valid SMBG profiles will be used for analysis. The excursion of SMBG for each meal category (that is, morning meal, midday meal, and evening meal) calculated using the average values at the corresponding time points will be used for analysis.

The following endpoints, collected from the MMTT, will be analyzed using the ANCOVA model with strata (country, type of basal insulin, use of metformin at study entry and HbA1c stratum) and treatment as fixed effects and baseline as a covariate:

- actual and change from baseline in fasting glucose (average of measurements at time 15 and 0), and PPG at 15, 30, 60, 120, 180, and 240 minutes after the meal
- PPG excursions at time 15, 30, 180, and 240 minutes after the meal (PPG minus fasting glucose)

Sensitivity analysis for PPG excursions may be performed to exclude patients whose PPG excursion could be affected by factors including MMTT consumption amount (for example, partial MMTT was consumed) and correction bolus insulin usage. A summary of the MMTT consumption and bolus insulin dose at baseline and Week 26 will be provided.

Treatment comparisons for the proportion of patients with HbA1c <7.0% and  $\le 6.5\%$  will be analyzed using a longitudinal logistic regression with repeated measurements conducted by a generalized linear mixed model including independent variables of treatment, baseline HbA1c value, visit, baseline HbA1c-by-visit interaction, and treatment-by-visit interaction. An unstructured covariance structure will be used. As a sensitivity analysis, the proportion of patients with HbA1c <7.0% and  $\le6.5\%$  at Week 26 (Visit 18), imputed using LOCF, will be compared using a logistic regression model with terms for treatment and baseline HbA1c value.

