10.3.3.2. Secondary Analyses

A graphical approach for multiple comparisons will be used to strongly control the overall Type I error (2-sided alpha level of 0.05) for testing the treatment effect for the primary and the following multiplicity adjusted objectives: superiority of LY900014 compared with insulin lispro for 1-hour PPG excursion at Week 26, 2-hour PPG excursion at Week 26, and change from baseline to Week 26 in HbA1c.

An ANCOVA model with strata (country, type of basal insulin, metformin use at study entry, and baseline HbA1c strata [\leq 8.5%, >8.5%]) and treatment as fixed effects and baseline as a

covariate will be used to analyze the 1-hour and 2-hour PPG excursions. However, if the percentage of the patients with missing MMTT data at baseline is higher than 15%, a constrained longitudinal data analysis model (Liu et al. 2009; Lu 2010) will be used instead. Analyses details will be documented in the SAP.

Hemoglobin A1c and change from baseline in HbA1c at all time points will be analyzed by the same MMRM model used for the primary analysis.

Additional continuous secondary efficacy variables, as well as the change from baseline for these variables, will be analyzed either by the MMRM or ANCOVA models described in Section 10.3.1.

Treatment comparisons for the proportion of patients with HbA1c <7.0% and \leq 6.5% will be analyzed using a longitudinal logistic regression with repeated measurements conducted by a generalized linear mixed model including independent variables of treatment, baseline HbA1c value, visit, baseline HbA1c by visit interaction, and treatment by visit interaction. An unstructured covariance structure will be used. As a sensitivity analysis, the proportion of patients with HbA1c <7.0% and \leq 6.5% at Week 26 (Visit 18), imputed using LOCF, will be compared using a logistic regression model including treatment and baseline HbA1c value in the model.

Actual and change from baseline in basal, prandial, and total dose, as well as the prandial/total insulin dose ratio, will be analyzed by the MMRM models described in Section 10.3.1.

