#### 5.3. Method of Assignment to Treatment

Patients who meet all criteria for enrollment will be randomized to double-blind treatment at Visit 8. Assignment to treatment groups will be determined by a computer-generated random sequence using an interactive web-response system (IWRS). Patients will be randomized to 1 of the 2 treatment groups in a 1:1 ratio. Stratification will be by country (China vs. Other), HbA1c stratum ( $\leq 8.5\%$  vs. >8.5% at Visit 7), type of basal insulin during the lead-in period (glargine U-100 vs. degludec U-100), and use of metformin at study entry (yes vs. no).

Abbreviation: T = telephone visit.

a At Visit 2, patients on insulin glulisine, insulin aspart, regular human insulin, or premixed insulin will be transferred to insulin lispro. The patients' basal insulin regimen will be switched to insulin glargine U-100 once daily or to insulin degludec U-100 once daily. At Visit 8, patients will be randomized to either premeal insulin lispro or premeal LY900014 and continue their basal insulin regimen.

- b Titrate basal insulin
- c Titrate prandial insulin (insulin lispro or LY900014)
- d Patients will discontinue study insulins at Week 26.

Figure 5.1. Illustration of study design.

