#### 6.2. Adjustments for Covariates

Stratification will be by country (China vs. Other), HbA1c stratum ( $\leq 8.5\%$  vs. >8.5% at baseline), type of basal insulin during the lead-in period (glargine U-100 vs. degludec U-100), and use of metformin at study entry (yes vs. no). Stratification factors will be entered into the IWRS for randomization and also collected in the database by electronic case report form (eCRF) or central laboratory. The analysis models for efficacy endpoints will use the stratification factors as collected in the database.

For continuous analyses of HbA1c, the stratification factor of HbA1c stratum (baseline) will not be included. Instead, the continuous value of baseline HbA1c will be included in the analysis models.

Other analyses will include the stratification factors as noted in Sections 6.11 and 6.12.

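### Both HbA1c target models omit three of the four randomization factors, unlike the other efficacy models; adding them, with a fallback rule, is a cheap improvement

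*SAP*

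**What the plan says.** SAP 5.3 sets out the randomization: "Stratification will be by country (China vs. Other), HbA1c stratum", basal insulin type during the lead-in, and metformin use at entry. That makes four factors.

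SAP 6.2 (Adjustments for Covariates) makes three statements about them:
- In general: "The analysis models for efficacy endpoints will use the stratification factors as collected in the database".
- For continuous HbA1c analyses the HbA1c stratum is dropped: "Instead, the continuous value of baseline HbA1c will be included in the analysis models".
- It closes: "Other analyses will include the stratification factors as noted in Sections 6.11 and 6.12".

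SAP 6.11.5 defines two models for the HbA1c targets. The main one is a longitudinal logistic mixed model "including independent variables of treatment, baseline HbA1c value, visit, baseline HbA1c-by-visit interaction, and treatment-by-visit interaction". In the LOCF sensitivity analysis the Week 26 proportions are "compared using a logistic regression model with terms for treatment and baseline HbA1c value". Protocol 10.3.3.2 lists the same terms for the longitudinal model, and for the LOCF analysis it also has the proportions "compared using a logistic regression model including treatment and baseline HbA1c value in the model".

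The primary HbA1c model in SAP 6.11.1, by contrast, includes "strata (country, type of basal insulin, use of metformin at study entry), visit, and treatment-by-visit interaction".

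**The concern.** The same HbA1c measurement is adjusted for country, basal insulin type and metformin use when analysed as a continuous variable, and is not adjusted for them once it is cut at 7.0% or 6.5%. Neither document gives a reason.

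Two things are at stake. The first is precision. When randomization is balanced within factors that predict the outcome, a model that omits them gives the analysis no credit for that balance. In logistic regression the test then becomes somewhat conservative, and the estimated odds ratio lies closer to 1 than the strata-adjusted one. The second is clarity. A programmer reading SAP 6.2 could put the factors in, and one reading only SAP 6.11.5 would leave them out. Attainment of HbA1c targets is a named secondary objective, so its model should not depend on which section is read.

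**Working it through.** **1. Terms side by side.** SAP efficacy models that list their terms:

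| Model | Country, basal insulin type, metformin | HbA1c stratum |
|---|---|---|
| HbA1c MMRM, primary (6.11.1) | yes | continuous baseline HbA1c |
| HbA1c ANCOVA with LOCF (6.11.3) | yes | continuous baseline HbA1c |
| 1-hour and 2-hour PPG excursion ANCOVA (6.11.2) | yes | yes |
| 1,5-AG, SMBG and insulin dose MMRM (6.11.5) | yes | yes |
| Other MMTT ANCOVAs (6.11.5) | yes | yes |
| ITSQ ANCOVA (6.11.6) | yes | yes |
| HbA1c targets, longitudinal logistic (6.11.5) | **no** | continuous baseline HbA1c |
| HbA1c targets, LOCF logistic (6.11.5) | **no** | continuous baseline HbA1c |

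Each target model therefore omits 3 of the 4 factors. The comparison is limited to models that list their terms: Table 6.3, for example, names only a method for each exploratory variable.

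**2. The plan's own sizing figure.** Inputs from SAP 5.2: margin 0.4, true difference 0, SD 1.1, 149 completers per arm, two-sided 95% CI.
- Standard error = 1.1 × √(2/149) = 0.1274.
- 0.4/0.1274 = 3.139; power = Φ(3.139 − 1.960) = Φ(1.179) = 0.881. The noncentral t with 296 df gives 0.879. Stated: 87%.
- 298/(1 − 0.15) = 350.6, so 351. Stated: about 350.

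Both figures reproduce, and neither depends on the target models. The documents give no power or responder rate for this endpoint, so the size of the effect can only be illustrated.

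**3. Illustrative simulation.**
- From the documents: 350 patients, 1:1 allocation, and 80% from China (280/350).
- Assumed: 30% on degludec, 10% on metformin; baseline HbA1c mean 8.0 and SD 0.8; log-odds −1.5 per 1% of baseline HbA1c; control responder rate about 22% to 23%; permuted blocks of four within all four strata.
- Each omitted factor shifts the log-odds by 0, 0.5 or 1.0 in absolute value.
- 3,000 trials per scenario. Each trial was analysed by single-visit logistic regression on treatment and baseline HbA1c, with and without the three factors.

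| Factor effect (log-odds) | Rejection under OR 1: without / with | Power at conditional OR 1.8: without / with | Estimated OR: without / with |
|---|---|---|---|
| 0 | 5.3% / 5.5% | 58.0% / 58.5% | 1.81 / 1.82 |
| 0.5 | 4.9% / 5.3% | 56.6% / 57.8% | 1.80 / 1.83 |
| 1.0 | 3.8% / 4.5% | 53.1% / 56.7% | 1.74 / 1.83 |

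- Power differences: 58.5 − 58.0 = 0.5; 57.8 − 56.6 = 1.2; 56.7 − 53.1 = 3.6 points.
- Monte Carlo standard error: √(0.05 × 0.95/3000) = 0.4 points for a rejection rate near 5%, and √(0.57 × 0.43/3000) = 0.9 points for power near 57%. Both models were fitted to the same trials, so their difference is better determined than either rate alone. Even so, the 0.5-point difference should be read as about zero.
- Mechanism in the last row: the standard error is smaller without the factors (0.270 against 0.282), but the estimate shrinks more. ln(1.743)/0.270 = 2.06, against ln(1.828)/0.282 = 2.14 with the factors.

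A second simulation used other assumed values: prevalences of 80%, 50% and 15%, treatment log-OR 0.55, and 1,500 trials. Power rose from 52.7% to 53.5% for factor effects of 0.4, rose from 47.3% to 50.0% for effects of 0.8, and did not change when the factors had no effect.

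**The case against.** Several points on the other side stand.

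- **Not all stratification is ignored.** A reader might infer that the models disregard the randomization altogether. They do not: continuous baseline HbA1c carries the HbA1c stratum, which is plausibly the factor most predictive of reaching an HbA1c target. SAP 6.2 states that substitution only for continuous HbA1c analyses, but the same reasoning applies here.
- **The conflict with SAP 6.2 is arguable.** A reader might call it a flat contradiction. The general sentence follows one saying that the factors are held both in the IWRS and in the database, so it can be read as choosing the data source. The closing sentence, "Other analyses will include the stratification factors as noted in Sections 6.11 and 6.12", can also be read as letting SAP 6.11.5 set its own terms.
- **The protocol has the same models.** SAP and protocol agree, so this is not drift between documents. Agreement does not supply a reason for the omission, however.
- **No false-positive risk or biased test follows.** A reader might infer an invalid result. The shift in the odds ratio is non-collapsibility: the model with fewer covariates targets a slightly different, more marginal odds ratio. Rejection under no effect did not exceed the nominal level by more than simulation error.
- **The fix is not wholly free.** The longitudinal model has an unstructured covariance, and SAP 6.11.5 gives no fallback for it. A small metformin group, or few patients at ≤6.5%, could cause separation or non-convergence. This is a fair objection to adding terms without a rule, but not to adding them with one.

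**Conclusion.** The point holds as a minor inconsistency in the choice of analysis. Both HbA1c target models omit country, basal insulin type and metformin use, while the other SAP 6.11 efficacy models that list their terms include them, and SAP 6.2 on its plain reading asks for them.

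If the three factors predict the outcome, the planned test is slightly conservative, loses about 0 to 4 points of power, and reports an odds ratio a little closer to 1. With the strongest effects assumed here, that is 1.74 against 1.83. If they do not predict it, nothing material changes. These sizes rest on assumed prevalences for basal insulin and metformin, assumed factor effects, an assumed responder rate and an assumed treatment effect. They come from a single-visit model rather than the repeated-measures model, and convergence of the latter was not tested.

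The endpoint is an other secondary objective, and SAP 6.5 makes no multiplicity adjustment for it. The noninferiority test and the multiplicity-adjusted superiority tests already include these factors and are unaffected.

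**What to change.** In SAP 6.11.5, add country, basal insulin type and metformin use as fixed effects to both target models, keeping continuous baseline HbA1c in place of the HbA1c stratum. Each factor has two levels, so this adds three 1-df terms.

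Prespecify what happens if a model does not converge or shows separation. For example, drop a factor with a sparse level, with the threshold fixed before unblinding. For the longitudinal model, also step through a stated order of simpler covariance structures, as SAP 6.11.1 does for the primary model.

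If the sponsor prefers to keep the models as they are, SAP 6.2 should name them as an exception and give the reason.

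The cost is wording only: no new data, visits or patients. The downsides are a slightly higher convergence risk, which the fallback covers, and a small departure from the terms listed in protocol 10.3.3.2. SAP 6.1 allows a change that does not touch a principal feature of the protocol to be described and justified in the SAP or the study report without an amendment.
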